7.2.3 Primary Analysis for Primary Endpoints

For primary endpoint analysis, non-inferiority for efficacy will be established if the upper limit of a two sided 95% confidence interval for the absolute difference (MYL-1501D Process VI minus Process V) of mean change from baseline to endpoint for HbA1c is no greater than 0.4% at Week 18. The primary analysis will be performed on the intent to treat (ITT) analysis set.

7.2.4 Secondary/Sensitivity Analyses for Primary Endpoints

A further robustness check will be conducted using the PP population and applying the same MMRM procedure as described in previous section to establish non-inferiority. Any differences in the conclusion will be further investigated by examining differences between the ITT and the PP populations.

Other sensitivity analysis addressing missing data will be conducted in the following manner:

Same analysis approach as primary analysis without imputing missing values.

In another method, the imputed values will be corrected such that the full non-inferiority margin will be added for imputed values in Process VI group. All imputed datasets will be analyzed using the same model parameters as used in the primary analysis, and the results will be combined using Rubin's rules.

A standard last observation carried forward (LOCF) approach will be conducted such that missing data will be imputed by LOCF. This dataset will be analyzed for the ITT and PP populations using the ANCOVA model for which details will be described in the SAP.

7.2.5 Missing Data

The only imputed data will be performed in the primary and sensitivity analyses as described above for HbA1c. Otherwise, missing data will not be imputed.

7.2.6 Sub-Group Analyses

Subgroup analyses of important factors, including but not limited to factors such as age group, gender and race are planned for the key outcomes of HbA1c and immunogenicity variables. These will be conducted by adding factor and treatment-by-factor interactions to the MMRM model models of the main analyses. Other exploratory subgroup analyses may be performed, as deemed appropriate.

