7.2.2 Statistical Methodology for Primary Endpoints

For the analysis of the primary endpoint all randomized subjects will be taken account – irrespective of whether subjects having post-baseline measurement. All scheduled non-missing data combined together with imputed missing data will be performed for primary analysis. Multiple imputed datasets will be generated based on the assumption of a monotone missing data pattern. The imputation will be performed using the monotone regression method for week 12 and week 18 sequentially. The variables treatment, pooled investigator, and basal insulin dose time will be used as independent variables.

Then the treatment effect will be estimated using a repeated measures analysis employing a restricted maximum likelihood (REML)-based, mixed model repeated measures (MMRM)-effects model approach. In this model all subjects will be used for the estimation of the 95% confidence interval of the difference between MYL-1501D Process VI product and Process V product for mean change in HbA1c at week 18. The MMRM model will include the fixed, categorical effect of treatment group assignment, visit, treatment group-by-visit interaction and the other fixed effect terms investigator, basal insulin dose time, and baseline HbA1c value as covariates.

Further details on the MMRM model will be provided in the SAP. Investigator pooling will be finalized before unblinding treatment to avoid introducing bias. The detailed method of investigator pooling will be documented in the SAP.

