Then, the remaining monotone missing data will be imputed using sequential regression multiple imputation, where a separate regression model is estimated for imputation of each variable (i.e., measurement at each visit) one after the other including the observed values and the values just imputed from the previous visit. Each regression model will include explanatory variables for pooled investigational sites, basal insulin dose time (morning vs. evening), treatment group and all previous (baseline (visit 6), week 12 (visit 12) and week 18 (visit 14)) values of HbA1c.

No rounding or range restrictions will be applied.

Imputed data will consist of 100 imputed datasets. The random seed number for the partial imputation with the MCMC method will be 20171220, and the random seed number for the sequential regression MI will be 171016.

Each of the 100 imputed datasets will be analyzed using the following analysis method. Change from baseline in HbA1c to each post-baseline visit will be calculated based on observed and imputed data. Mean changes from baseline in HbA1c values will be analyzed using a mixed model for repeated measures (MMRM) approach. Restricted maximum likelihood (ReML) estimation will be used. The MMRM model will include the changes from baseline in HbA1c values as dependent variables, the baseline HbA1c values as fixed covariate, pooled investigational sites, basal insulin dose time (morning vs evening), treatment group (MYL 1501D Process V and MYL 1501D Process VI), visit (week 12 and week 18), and treatment group by visit interaction as fixed effects, and subjects as random effect. An unstructured covariance structure will be used to model the within-subject error and the Kenward-Roger approximation will be used to estimate the degrees of freedom. If this analysis fails to converge, the following covariance structures will be tested: AR(1), ARH(1), CS, CSH, TOEP, TOEPH. The covariance structure converging to the best fit, as determined by Akaike's information criteria (AIC) will be used as the primary analysis.

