16.2.4. SUBGROUP ANALYSIS

The effect of subgroups mentioned in [section 8.6](#) on the change from baseline HbA1c at week 18 will be examined by employing a MMRM model. The subgroups will be included in the model along with the treatment group. Additionally separate subgroup analysis within each subgroup mentioned in [section 8.6](#) will be performed same MMRM model for treatment comparison within each subgroups.

The similar subgroups will also be examined for the immunogenicity parameters for the percent binding and the incidence analysis of cross reactive antibody. Besides examine subgroup by treatment interaction for percent binding. Separate analysis for both percent binding and incidence will be performed for treatment comparison within each subgroup.

Document:	\sasdata\Mylan\Insulin_glargine\SYA22825\Biostatistics\Documentation\SAP\MYL-1501D-3004_SAP_Final_2_0_clean.doc		
Author:	[name]	Version Number:	2.0
		Version Date:	18OCT2018
Template No:	CS_TP_BS016 Revision 4	Reference:	CS_WI_BS005
Effective Date:	01Apr2016		

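### The HbA1c subgroup interaction in Protocol 7.2.6 is averaged over Weeks 12 and 18, although SAP 16.2.4 sets the target at Week 18

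*Protocol*

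**What the plan says.** Protocol 7.2.6 plans subgroup analyses of HbA1c and immunogenicity by age group, gender, race and possibly other factors. On the method it says: "These will be conducted by adding factor and treatment-by-factor interactions to the MMRM model models of the main analyses".

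The main model is set out in Protocol 7.2.2: "The MMRM model will include the fixed, categorical effect of treatment group assignment, visit, treatment group-by-visit interaction", plus investigator, basal insulin dose time and baseline HbA1c. SAP V2.0 section 16.1.3 fixes the visits and the structure: "visit (week 12 and week 18), and treatment group by visit interaction as fixed effects, and subjects as random effect". It adds: "An unstructured covariance structure will be used to model the within-subject error".

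SAP V2.0 section 16.2.4 states the target for HbA1c. The effect of the subgroups "on the change from baseline HbA1c at week 18 will be examined by employing a MMRM model". On the terms it says only: "The subgroups will be included in the model along with the treatment group". It also plans a separate analysis inside each subgroup, which "will be performed same MMRM model for treatment comparison within each subgroups". For percent binding it names a subgroup-by-treatment interaction and, again, separate analyses within subgroups.

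Neither document names a factor-by-visit or treatment-by-factor-by-visit term, and the code in SAP Appendices 3 and 4 contains no subgroup model. SAP section 4.3 reports no changes from the protocol's analyses.

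**The concern.** The main model lets the treatment effect differ between Week 12 and Week 18. The subgroup extension does not let the subgroup difference in treatment effect do the same: it forces one value on both visits. The coefficient that results is not the Week 18 interaction unless the interaction happens to be equal at the two visits.

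The error can run either way. An interaction that emerges by Week 18 is diluted by a smaller Week 12 value, and one present at Week 12 that has faded by Week 18 is reported as if it persisted. The same structure applies to percent binding, which is sampled after baseline at Weeks 2, 6, 12 and 18, so early visits enter that average too.

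**Working it through.** **Inputs.** The SD of change in HbA1c to Week 18 is 0.74 (Protocol 7.1). The two visits and the unstructured covariance come from SAP 16.1.3. The Week 12 SD (s12) and the between-visit correlation (r) are not in the documents and are varied below as assumptions.

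**The plan's own figure.** The plan gives no figure for the interaction. The SD of 0.74 does fit its sample size: with margin 0.4, true difference 0.03 and one-sided 2.5%, a noncentral-t calculation gives power 0.8999 at 85 per arm and 0.903 at 86. The stated 86 per arm (172 in total) therefore reproduces.

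**Weights.** With complete data, intercepts and treatment effects are visit-specific and the factor and treatment-by-factor effects are common. Generalised least squares then estimates the common interaction as w12 × (Week 12 interaction) + (1 − w12) × (Week 18 interaction), where

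w12 = (s18² − r·s12·s18) / (s12² + s18² − 2·r·s12·s18).

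For s12 = 0.60, s18 = 0.74, r = 0.7: (0.5476 − 0.3108) / (0.36 + 0.5476 − 0.6216) = 0.2368 / 0.286 = 0.83.

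| Week 12 SD (assumed) | r = 0.5 | r = 0.6 | r = 0.7 | r = 0.8 | r = 0.9 |
|---|---|---|---|---|---|
| 0.60 | 0.70 | 0.75 | 0.83 | 0.98 | 1.37 |
| 0.65 | 0.63 | 0.66 | 0.71 | 0.81 | 1.10 |
| 0.70 | 0.56 | 0.57 | 0.59 | 0.64 | 0.77 |
| 0.74 | 0.50 | 0.50 | 0.50 | 0.50 | 0.50 |
| 0.80 | 0.42 | 0.40 | 0.37 | 0.31 | 0.12 |

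The weight on Week 12 is near 1 only when s12/s18 is close to r; for example 0.60/0.74 = 0.81 with r = 0.8. A weight above 1 means that Week 18 enters with a negative sign.

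**What this does to an estimate.** Take a true interaction of 0.4% at Week 18 and none at Week 12. The expected estimate is 0.4 × (1 − 0.50) = 0.20% at equal SDs, and 0.4 × (1 − 0.98) = about 0.01% at s12 = 0.60 and r = 0.8.

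**Simulation check.** N = 202, a 50/50 binary factor, complete data, unstructured covariance, r = 0.8, 2000 replicates per case, two-sided 5%. Each cell gives the mean estimate and the rejection rate.

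| True interaction | s12 | Protocol model | Week 18 contrast |
|---|---|---|---|
| 0.60 at Week 18 only | 0.74 | 0.31, 35% | 0.61, 82% |
| 0.60 at Week 18 only | 0.65 | 0.11, 12% | 0.60, 81% |
| 0.60 at Week 18 only | 0.60 | 0.02, 7% | 0.60, 82% |
| 0.60 at Week 12 only | 0.74 | 0.29, 33% | 0.00, 5% |
| 0.60 at Week 12 only | 0.60 | 0.59, 92% | 0.00, 5% |

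**Precision given up by the Week 18 contrast.** The SE of the common coefficient relative to that of the Week 18 interaction is √[s12²(1 − r²) / (s12² + s18² − 2·r·s12·s18)]. At equal SDs this is √[(1 + r)/2] = 0.89 to 0.95 for r = 0.6 to 0.8, so the Week 18 interval is wider by 1/0.95 to 1/0.89, about 5 to 12%. At s12 = 0.60 the ratio is 0.78 to 0.81 over the same correlations, which makes the interval up to about 28% wider.

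**The case against.** The strongest objection is that SAP 16.2.4 already answers the Week 18 question by another route. The model fitted inside each subgroup keeps treatment-by-visit, so it yields a Week 18 difference between Process VI and Process V with an interval for every subgroup. A reader might infer that an interaction emerging by Week 18 would go unseen. That does not follow, because it would show in these estimates. What they do not supply is an estimate, interval or test of the Week 18 interaction itself.

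Second, Protocol 7.2.6 is a one-sentence outline, Protocol section 7 leaves detail to the SAP, and for HbA1c the SAP does not name an interaction term. The visit structure of the fitted model is therefore partly open. But the one rule that is written gives a visit-averaged coefficient, and the SAP declares no departure from it.

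Third, the weights rest on undocumented inputs. A reader might infer that the interaction is almost entirely a Week 12 result. The documents do not support that: it needs an SD ratio close to the correlation, and neither quantity is given. At a Week 12 SD of 0.80 the Week 12 weight falls to between 0.42 and 0.12.

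Fourth, an interaction of exactly zero at Week 12 is an extreme case. If it were 0.3% at Week 12 and 0.4% at Week 18, the common estimate would be 0.35% at weight 0.50 and about 0.30% at weight 0.98. For percent binding, linear growth with equal visit weights would give (2 + 6 + 12 + 18)/(4 × 18) = 0.53 of the Week 18 value, but nothing in the documents supports either assumption, so that size is unknown.

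Finally, SAP 8.6 says that the study was not designed for high power within subgroups. With SD 0.74, 202 subjects and a 50/50 factor, the Week 18 interaction has SE 0.74 × √(4/50.5) = 0.21, so an interaction of 0.4% has only about 48% power even in the right model. A common interaction is also a recognised parsimonious choice. These points limit the importance of the defect; they do not make the coefficient a Week 18 quantity.

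**Conclusion.** The concern holds, and it is minor. The interaction that Protocol 7.2.6 specifies does not estimate the Week 18 target in SAP 16.2.4. That follows from the model terms and needs no assumption about the data. The size does: the consequence ranges from halving a Week 18-only interaction at equal SDs to nearly removing it at a Week 12 SD of 0.60 with correlation 0.8, and it is milder than halving if Week 12 is the more variable visit. The weights are exact for complete data.

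The primary non-inferiority analysis and the per-subgroup Week 18 effects are unaffected. For percent binding the same averaging applies, over four visits.

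**What to change.** In Protocol 7.2.6 and SAP 16.2.4, specify that the subgroup model contains factor, treatment-by-factor, factor-by-visit and treatment-by-factor-by-visit, in addition to the terms of the main model. Name the quantity to be reported: the difference between subgroups in Process VI minus Process V at Week 18, with its 95% CI. State the interaction explicitly for HbA1c in the SAP, and give the percent-binding model the same visit terms and the same Week 18 contrast. Keep the separate within-subgroup models as planned.

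No new data are needed. With two visits, a factor with k levels costs 2 × (k − 1) extra coefficients, so two for a binary factor. The price is the wider interval worked out above, which is the actual uncertainty about the Week 18 interaction.

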7.3 Secondary Endpoints

The following efficacy measures (both actual and change values) will be summarized at baseline and scheduled visit. Similar statistical analysis approach for primary will be performed for continuous variables without imputing missing values. Contrasts of LS mean at each scheduled visit will be used to evaluate all pairwise treatment comparisons, and 95% confidence intervals for treatment differences in LS means will be computed for each visit.

- Change in fasting plasma glucose from baseline
- Change in basal insulin, meal-time, and total insulin dose per unit body weight (U/kg) from baseline
- Change in 8-point SMBG profile from baseline.

All above analyses will be performed on ITT set.

The following safety measures (both actual and change values) will be summarized at baseline and scheduled visit. Contrasts of LS mean at each scheduled visit will be used to evaluate all pairwise treatment comparisons, and 95% confidence intervals for treatment differences in LS means will be computed for each visit. For categorical data analyses, Fisher's exact test or Chi-squared test will be used. The details will be provided in the SAP.

- Incidence of positive antibody response and change in antibody percentage binding from baseline.
- Change in hypoglycemia rate (30 day adjusted) from baseline and incidence of hypoglycemic events
- Incidence of treatment-emergent adverse events (TEAEs) and serious adverse events (SAEs)
- Incidence of local allergic reactions, systemic allergic reactions and other adverse events
- Incidence of device-related safety assessment

The incidence of subjects with each of the three following criteria will be summarized descriptively (for categorical measures) by treatment to explore possible insulin neutralization effect:

- An increase of over 10% in cross reacting antibodies from baseline
- Increases in HbA1c of over 0.2% from baseline at any visit
- Increase in total or basal insulin dose at any visit

The total incidence of Device-related safety events will be summarized for each treatment group and would include device-related TEAEs and events related to device complaints or failures. For device-related TEAEs, two categories will be summarized for each treatment: needle-related TEAEs such as pain, bruise, and bleeding; and other device-related TEAEs, such as hyperglycemia or hypoglycemia. For confirmed device-related malfunctions or failures, incidence will be listed and summarized for each treatment.

All above analyses will be performed on safety set.

7.4 Analysis Set Definitions

The ITT analysis set includes all randomized subjects (including subjects who receive incorrect treatment, do not complete the study or do not comply with the protocol or used prohibited medication).

The PP analysis set includes subjects who complete Week 18, and have HbA1c measurements as per the protocol, or have at least one post-baseline HbA1c data (for subjects who discontinue prematurely); and do not have protocol violations that impact the primary

outcome (as detailed in the statistical analysis plan). Subjects who meet rescue medication criteria and take rescue medication will be excluded from PP analysis set. The subjects excluded from the PP population will be identified before database lock (i.e., before unblinding the study team).

The safety analysis set includes subjects who take at least one dose of the study medication after randomization. For safety analyses, subjects will be categorized according to the treatment that they actually received.

7.5 Other Safety Analyses

The analysis set for safety summaries is defined as all subjects who received at least one dose of study medication in the randomized treatment period. Safety data from the run-in period will be presented in listings only.

Treatment emergent adverse events and concomitant medications will be summarized and listed. All AEs that occur after the first dose of double-blind study medication through 14 days after the last dose will be considered treatment emergent AEs. The number and percentage of subjects with at least one treatment emergent AE will be presented by treatment group and events further summarized by maximum severity and relationship to study medication.

Descriptive statistics will be provided for the following safety data. No inferential analysis of this safety data is planned. Any ECG, blood pressure, and pulse rate abnormalities of potential clinical concern will be described.

7.5.1 Vital Signs

Change from baseline of vital sign measurements will be analyzed using MMRM with model terms of pooled investigator, basal insulin dose time, treatment, visit, treatment-by-interaction as fixed effects, and baseline value as covariate. The descriptive statistics including actual measurement and change from baseline along with treatment comparison will be performed at scheduled visits.

The percentage of subjects in categories such as potentially clinically significant will be summarized and treatment comparison will be performed using Fisher's exact test.

7.5.2 ECG Analyses

The percentage of subjects in categories such as abnormal/non-clinically significant and abnormal/clinically significant will be summarized and treatment comparison will be performed using Fisher's exact test.

7.5.3 Laboratory Data

Change from baseline of laboratory measurements will be analyzed using MMRM with model terms of pooled investigator, basal insulin dose time, treatment, visit, treatment-by-visit interaction as fixed effects, and baseline value as covariate. The descriptive statistics for actual measurement and change from baseline along with treatment comparison will be performed at scheduled visits.

The percentage of subjects in categories such as abnormal/non-clinically significant and abnormal/clinically significant will be analyzed using Fisher's exact test. P-value for the two-sided test will be presented.

8 ADMINISTRATIVE PROCEDURES

8.1 Source Documentation Forms

All clinical data will be recorded by the clinical staff on raw data sheets and/or recorded electronically using validated software. If computerized systems are used to create, modify, maintain, archive, retrieve or transmit source data, they must comply with the applicable regulatory regulations and/or guidance.

The nature and location of all source documents will be documented separately. Source data may be directly captured from devices, transferred from 3rd parties (e.g. laboratory data) or entered manually into CRF/database.

8.2 Access to Data/Source Documentation

The Investigator or designated representative will permit full access to data and source documentation for the purpose of clinical monitoring, audits, IRB/IEC review and regulatory inspections.

8.3 Final Clinical Study Report and Case Report Forms (CRFs)

A written clinical study report will be provided in accordance with the International Conference on Harmonization (ICH) E-3 guidelines including Annex I (Synopsis) documenting the clinical execution of the study. This report will include a description of any protocol deviations. The final report will also include reasons for withdrawals and any necessary treatment(s). The report will also include tables presenting demographics (separate summary tables for enrolled and completed subjects), and adverse events recorded during the study. In addition, the clinical study report will include a Quality Assurance statement, documenting that the report has been reviewed for completeness, accuracy, and compliance with the protocol and applicable local and federal regulations. For final clinical reporting purposes only, adverse events deemed “definite”, “probable” or “possible” will be included in the treatment-related summaries/listings.

Case Report Forms containing data transcribed from subject source documents (as appropriate) and copies of other source documents will be supplied by the clinical site. The Principal Investigator must sign each subject’s CRF after completion of data entry, signifying that the data entered in the CRF is complete and accurate. Electronic CRFs may be provided.

8.4 Adherence to Protocol

Except for an emergency situation in which proper care for the protection, safety and well-being of the study subjects requires medical treatment, the study will be conducted as described in the approved protocol (and amendments, if applicable), GCP and applicable SOPs. In addition, the study will be conducted in accordance with the applicable regulatory requirements of the country where the study is being conducted as well as the country where the study will be submitted. Any deviation(s) from the protocol will be recorded and presented in the final report.

